### **Intervention Risks:**

To date there have been no serious complications reported in the literature associated with BDET. Complications of the procedure are rare and no major complications have been reported. The dilatation will be performed under general anaesthesia and so patient discomfort and distress will be greatly mitigated.

Reported complications include bleeding, surgical emphysema (air bubbles) of the parotid (angle of jaw) region (0.2% chance and temporary in every case) and temporary tinnitus. Although rare, any procedure involving the ear carries a risk of increased hearing loss, dizziness, tinnitus and facial palsy.

Potential complications (that have not been reported so far) include: regional nerve damage, ossicular disruption/hearing loss, carotid artery injury and associated cerebrovascular accident. All of these risks will be discussed as part of the informed consent procedure.

### **Follow up and Therapeutic Cross Over**

Patients will be followed up at 2, 6, 12, and 24 week intervals, examination and diagnostic testing will take place at each of these time point as detailed in Table 1.

At the 6-week follow up, participants initially randomized to the control group will be given the opportunity to cross over to the intervention group in consultation with their consulting surgeon. After crossover, participants will be followed up at the post intervention intervals of 2, 6, 12, and 24 weeks and undergo the testing and examination as outlined in table 1. Participants who chose to crossover will be consented for the procedure and informed regarding the required follow up.

## **End Points and Statistical analysis**

The **primary** effectiveness endpoint will be normalization of tympanometry (to type A) at 6-week follow-up.

Investigators and a blinded, independent evaluator, unaffiliated with the patients' care will review all tympanograms. When findings between investigator and evaluator area inconsistent, a second independent evaluator will conduct a tie-breaking assessment. Each patient will serve as the unit of analysis; for a bilaterally treated patient, both ears tympanograms have to normalise for that patient to be considered a success.

The **secondary** end point will be normalisation of ETDQ-7 scores (<2.1) at 6-week follow up.

Data from all investigations undertaken will be collated at each follow up appointment for each patient. Analysis of the collated non-identifiable data will be undertaken using a statistical analysis package (e.g. SPSS)

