### **Proposed Interventions and Treatment Arms:**

#### **Group 1 (balloon dilatation + medical management)**

Balloon dilation of the ET will be performed under general anesthesia in the operating room by trained and accredited otolaryngologists as recognized by the Royal Australian College of Surgeons (RACS). All of the surgeons involved in the study are skilled in the proposed procedure and have performed multiple successful balloon dilatations of the eustachian tube for the treatment of ETDD prior to the commencement of the study.

Each ET dilatation will be performed using a standardized technique. Patients will receive general anesthesia by a accredited anaesthetist. The nasal cavity on the affected side will be decongested using 3mls of oxymetazoline instilled into the nasal cavity. If the patient is undergoing bilateral dilatation then both nasal cavities will be decongested. Rigid nasendoscopy will be used in all cases to allow examination of the nasal cavity and facilitate safe and accurate placement of the balloon catheter into the ET.

With the aid of nasendoscopy, a single use introducer will inserted into the nasal passage on the affected side so that it passes to the back of the nasal cavity and nasopharynx. The angled introducer is then pointed towards the affected ET opening. A single use catheter with a balloon tip is then inserted through the introducer and emerges from the angled end into the opening of the ET. The catheter is then advances into the ET under visualization until the indicator line on the catheter emerges from the introducer, signifying that the catheter has been sufficiently advanced. The balloon is then inflated with sterile isotonic saline solution (NaCl 0.9%) for a period of 2 minutes using the included insufflator, to an inflation pressure of 10 to 12 atmospheres while the balloon is held in situ. At the conclusion of the 2-minute period, the balloon is deflated and pulled back out of the ET so that it re-enters the introducer. The balloon catheter and introducer are then removed together from the nasal cavity. If the patient has bilateral disease and both ETs require treatment, the procedure is repeated on the other side in the same way.

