## **Group 2 (medical management alone)**

Patients randomized to medical management alone will commence the same mometasone nasal steroid spray regimen for a planned period of 6 weeks on the day of randomisation. Again, continuation of therapy after the 6-week period will be at the discretion of the patient's surgeon.

Throughout the duration of study participation, subjects will be permitted to continue any concomitant medications for their ETDD or other medical conditions (i.e., allergic rhinitis, laryngopharyngeal reflux) deemed clinically necessary, per their surgeon's discretion. Subjects will not be permitted to start any new medications or to increase the dose or frequency for existing concomitant medications. Patients requiring such alterations or the commencement of new medications for medically indicated reasons will be excluded from the study.

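### The investigator's reading counts towards the primary tympanogram classification and decides every trace on which the two evaluators would split, in a trial where the investigator very probably knows the arm

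*Protocol*

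**What the plan says.** All the reading rules are in the protocol section End Points and Statistical analysis. The primary "effectiveness endpoint will be normalization of tympanometry (to type A) at 6-week follow-up" is a yes/no outcome per patient. On who reads: "Investigators and a blinded, independent evaluator, unaffiliated with the patients' care will review all tympanograms". On disagreement: "When findings between investigator and evaluator area inconsistent, a second independent evaluator will conduct a tie-breaking assessment". On patients treated on both sides: "both ears tympanograms have to normalise for that patient to be considered a success".

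Three other sections bear on what the investigator knows:

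- Group 1: "Balloon dilation of the ET will be performed under general anesthesia in the operating room".
- Group 2: "Patients randomized to medical management alone will commence the same mometasone nasal steroid spray regimen". No sham procedure is described.
- Follow up and Therapeutic Cross Over: at the 6-week visit, "participants initially randomized to the control group will be given the opportunity to cross over to the intervention group", in consultation with their surgeon. This is also the visit of the primary endpoint.

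**The concern.** In an open surgical trial, blinded reading of an instrument trace is the main protection the primary endpoint has. The secondary endpoint, the ETDQ-7, is reported by patients who know what they received. The protocol provides a blinded evaluator unconnected with care, but that evaluator's reading does not settle the classification. It must be matched by the investigator's, and if it is not, the trace goes to another reader. The blinding and the independence from care are attributed to the evaluator, not to the investigators. The second evaluator is called independent, with blinding not mentioned.

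If the investigator's view of a doubtful trace is coloured by knowing the arm, part of an observed difference in normalisation could come from reading rather than from treatment. The protocol itself fixes this rule for its only primary endpoint, so it is not a detail left open for later.

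**Working it through.** **Inputs from the protocol.** Two readings per trace, a third only on disagreement, and 75 patients split 2:1 (75 × 2/3 = 50 and 75 × 1/3 = 25, as stated). The protocol gives no figure for reader agreement or for the share of doubtful traces, so there is no stated figure to reproduce on this point.

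**Step 1: what the rule does.** Let I, E1 and E2 be the readings of the investigator, the first evaluator and the second evaluator, each A or not-A. The final reading is E1 if I = E1, and E2 otherwise.

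| I | E1 | E2 | Final |
|---|---|---|---|
| A | A | A | A |
| A | A | not-A | A |
| A | not-A | A | A |
| A | not-A | not-A | not-A |
| not-A | A | A | A |
| not-A | A | not-A | not-A |
| not-A | not-A | A | not-A |
| not-A | not-A | not-A | not-A |

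The result equals a two-of-three majority in all eight rows. In the four rows where E1 and E2 agree, the investigator changes nothing. In the four where they differ, the final reading is always the investigator's. E2 need not actually be consulted: when I agrees with E1, a potentially dissenting E2 is never asked.

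**Step 2: effect on one borderline trace.** Let p be the chance that an evaluator reads A (evaluators independent, ignorant of the arm) and q the chance that the investigator does.

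P(final A) = q[1 − (1−p)²] + (1−q)p² = p² + 2p(1−p)q

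The difference between arms is therefore 2p(1−p) × (q in Group 1 − q in Group 2). It is largest when the investigator always reads A in one arm and never in the other.

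| p | q = 1 | q = 0 | Difference 2p(1−p) |
|---|---|---|---|
| 0.3 | 0.51 | 0.09 | 0.42 |
| 0.5 | 0.75 | 0.25 | 0.50 |
| 0.7 | 0.91 | 0.49 | 0.42 |

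With a half-strength lean (q = 0.75 against 0.25) at p = 0.5: 0.625 − 0.375 = 0.25.

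**Step 3: averaged over all traces.** Multiply by the borderline share b (assumed; clear traces contribute nothing), at p = 0.5.

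| b | Full lean: 0.50 × b | Half-strength lean: 0.25 × b |
|---|---|---|
| 10% | 5 points | 2.5 points |
| 20% | 10 points | 5 points |
| 30% | 15 points | 7.5 points |

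If the reader whose vote decides does not know the arm, q is the same in both arms and the difference is 0 for any p and b.

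**Step 4: what that could do to a test.** This illustration counts one trace per patient, 50 against 25, no true difference, and a two-sided 5% pooled z-test enumerated exactly. Type-A rates of 10% to 30% among clear traces are assumed. With no reading bias the rejection rate is 4.5% to 5.1%. With a full lean and b from 10% to 30%, it is about 7% to 29%. With a milder lean (q = 0.7 against 0.3, giving 0.6 − 0.4 = 0.20 on a borderline trace and 2 to 6 points overall), it is about 5% to 8%.

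**Step 5: from trace to patient.** Steps 3 and 4 are not the bias in the endpoint as defined, because a patient treated on both sides needs both ears to be type A. A disputed ear does not matter if the other ear clearly fails, and it decides the patient if the other ear clearly passes. A patient with two treated ears also has two chances of a disputed trace. The protocol does not give the share of bilateral patients, so the net change cannot be computed.

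**The case against.** The protocol already goes further than many open trials: a blinded evaluator reads every trace and an independent one resolves disagreements. Several stronger readings are tempting, and the text does not support them.

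- A reader might infer that the investigator's vote is binding. It is not. Every final reading needs at least one evaluator on the same side.
- A reader might take the protocol to say that the investigator is unblinded. It does not say so, nor that the reading investigator is the one who treated that patient. This is an inference. It is strong, given surgery against spray, no described sham and a crossover discussion at the very visit of the endpoint, but it remains an inference.
- A reader might conclude that the tie-breaker is unblinded. Blinding is unstated for that reader, not denied, and someone of the same kind as the first evaluator is a natural reading.
- A reader might quote 5 to 15 points as the bias in favour of the device. Those are per-trace ceilings under an assumed borderline share, an extreme lean, and the value of p that makes the effect largest. The direction is a presumption, and the protocol declares no conflicts of interest.

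It can also be said that, if the blinded evaluator's reading is stored separately, an analysis on that reading alone can be run later, and that relying on one reader gives up a check on that reader's errors.

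All of this limits the size and certainty of the point. It does not remove the mechanism: the rule gives the decision to the investigator exactly where the evaluators would split, and a later re-analysis would not be the primary endpoint as the protocol now defines it.

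**Conclusion.** The concern stands in a limited form. By the logic of the rule, with no outside figure needed, the investigator's reading is counted and is decisive whenever the two evaluators would differ. Knowledge of the arm, which the investigator very probably has, can therefore influence borderline traces in the primary endpoint. The possible arm difference on such a trace is bounded by 2p(1−p), hence by 50 points. Averaged over all traces it is at most 5 to 15 points if 10% to 30% are borderline, and 2.5 to 7.5 points with a half-strength lean at p = 0.5. The borderline share, p and the lean are assumptions; the true size is unknown and could be small, and the per-patient effect may differ. This is a weakness that should be fixed, because it touches the only primary endpoint and is cheap to remove. It is not evidence that the endpoint is invalid.

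**What to change.** State in End Points and Statistical analysis that only blinded readings set the primary endpoint. The blinded evaluator's reading, on traces stripped of patient identity, arm and visit, is the one used. The second evaluator, stated to be blinded too, reads only traces the first cannot classify. Keep the investigator's reading for care and for a sensitivity analysis, with no role in the endpoint.

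The cost is mainly wording and the masking of traces, since both evaluators are already planned. The downside is that most traces would then rest on one contributing read, and a category for unclassifiable traces has to be defined. If double reading is wanted, two blinded evaluators can read every trace with a blinded tie-breaker, at the price of an extra blinded read per trace and a third blinded reader for splits.

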### **Publication and Dissemination:**

The findings of the proposed research project will be submitted for consideration of publication in peer-reviewed otology specific and general otolaryngology journals. The content will also be disseminated via presentation at regional, national and international meetings.

### **Conflicts of Interest:**

None of the investigators have any conflicts on interests associated with the proposed research project.

**Appendix 1:  
Eustachian Tube Dysfunction Questionnaire**

**The Seven-Item Eustachian Tube Dysfunction Questionnaire.**

Over the past 1 month, how much has each of the following been a problem for you?	No Problem	Moderate Problem	Severe Problem				
1. Pressure in the ears?	1	2	3	4	5	6	7
2. Pain in the ears?	1	2	3	4	5	6	7
3. A feeling that your ears are clogged or "under water"?	1	2	3	4	5	6	7
4. Ear symptoms when you have a cold or sinusitis?	1	2	3	4	5	6	7
5. Crackling or popping sounds in the ears?	1	2	3	4	5	6	7
6. Ringing in the ears?	1	2	3	4	5	6	7
7. A feeling that your hearing is muffled?	1	2	3	4	5	6	7

Reference: McCoul, E. D., Anand, V. K., & Christos, P. J. (2012). Validating the Clinical Assessment of Eustachian Tube Dysfunction: The Eustachian Tube Dysfunction Questionnaire (ETDQ-7). *The Laryngoscope*, 122(5), 1137-1141. <http://doi.org/10.1002/lary.23223>

